**Utilizing qualitative and quantitative methods to understand a new
model of Type 1 and 2 SLE**

NCT05426902

Document Date: May 9, 2019

Research Summary

Version Date: 09May2019

Protocol Title: Utilizing qualitative and quantitative methods to understand a new model of Type 1 and 2 SLE

Department/Division/Clinical Setting: Division of Rheumatology & Immunology, Duke University Medical Center.

Key Personnel: PI: [name], Assistant Professor, Division of Rheumatology & Immunology, Duke University Medical Center.

CRC: [name]

Co-Investigators:

Name: [name]

Title: Associate Professor of Medicine

Department: Medicine – Rheumatology & Immunology

Name: [name]

Title: Professor of Medicine

Department: Medicine – Rheumatology & Immunology

Name: [name]

Title: Associate Professor in Population Health Sciences

Department: Population Health Sciences

Name: [name]

Title: Consulting Professor in Population Health Sciences

Department: Population Health Sciences

Name: [name]

Title: Assistant Professor in Population Health Sciences

Department: Population Health Sciences

Name: [name]

Title: Assistant Professor of Medicine

Department: Medicine – Rheumatology & Immunology

Name: [name]

Title: Associate Professor of Medicine

Department: Medicine – Rheumatology & Immunology

Name: [name]
Title: Assistant Professor of Medicine
Department: Medicine – Rheumatology & Immunology
[REDACTED]

Name: [name]
Title: Medical Instructor in the Department of Medicine
Department: Medicine – Rheumatology & Immunology
[REDACTED]

Name: [name]
Title: Assistant Professor of Medicine
Department: Medicine – Rheumatology & Immunology
[REDACTED]

Project Leaders:

Name: [name]
Title: Clinical Trials Project Leader
Department: Population Health Sciences
[REDACTED]

Name: [name]
Title: Research Program Leader
Department: Population Health Sciences
[REDACTED]

Purpose of the Study:

The aims of this study are to:

1. Identify lupus patients' experiences with physician-reported and patient-reported signs and symptoms of SLE, and modify the Type 1 and 2 SLE conceptual model to reflect patients' experiences.
2. Develop a preliminary parsimonious measure to rapidly assess Type 1 and 2 SLE activity; and
3. Conduct a pilot implementation study of the Type 1 and 2 SLE model into clinical care in Duke Rheumatology.

Background & Significance:

Systemic lupus erythematosus (SLE) is a prototypic autoimmune disease whose heterogeneity has confounded scientists, clinicians, and patients for decades. Current therapeutic efforts are directed at the inflammation that causes organ damage, yet patients often remain disabled by fatigue, myalgia, mood disturbance, and cognitive dysfunction. These symptoms are persistent and often resistant to immunosuppression.

At Duke, we have developed a new conceptual model that characterizes SLE activity into two dimensions:

- Type 1: Classically considered SLE activity and recorded in physician-reported measures of SLE activity. Includes synovitis, rashes, serositis, nephritis, CNS lupus, and other objective signs.
- Type 2: Symptoms of fatigue, myalgia, mood disturbance, and cognitive dysfunction; typically not included in physician-reported measures of SLE, but are frequently reported by patients. Physicians

may ascribe these symptoms to depression or fibromyalgia, while patients identify them as SLE-related.

We hypothesize that Type 1 and 2 SLE activity varies in intensity over time, including some periods of minimal activity (neither Type 1 or 2) and mixed activity (both Type 1 and 2).

Patient-reported measures have had limited acceptance in the study of SLE, possibly due to the incongruence between Type 1 physician-reported activity and Type 2 patient-reported symptoms. According to over 1000 patients with SLE, a patient-defined-flare includes extreme fatigue (87% of the flares), aching joints (80%), muscle weakness or pain (74%), and forgetfulness (61%). Of these symptoms, only aching joints would be counted as active lupus by a rheumatologist; the remaining symptoms are likely Type 2 activity of SLE. While the authors of this study suggested that we need to re-educate our patients about lupus flares, we suggest we change how we think about SLE.

We are currently piloting two patient-reported outcomes (PRO) measures for Type 1 and 2 SLE: The Fibromyalgia Severity Score (FSS) allows patients to indicate areas of pain, extent of fatigue, waking unrefreshed, and cognitive symptoms. The FSS was designed to diagnose fibromyalgia, but we have found this scale clinically useful to efficiently measure the current extent of Type 2 SLE symptoms. The Systemic Lupus Activity Questionnaire (SLAQ) is a 24-symptom patient-reported measure of SLE activity. It partially correlates with the physician-reported Systemic Lupus Activity Measure. We have found the SLAQ clinically useful in highlighting important symptoms for patients, but the current scoring system combines Type 1 and 2 SLE activity, resulting in an assessment that is not clinically actionable.

The proposed research will build a brief preliminary PRO measure that combines features of the FSS and the SLAQ to indicate the current degree of Type 1 and Type 2 SLE activity, allowing for rapid assessment and appropriate treatment in practice.

The overall objective of this study is to develop a composite measure based on our conceptual model of Type 1 and 2 SLE to distinguish between these two symptom complexes, and then conduct a pilot implementation study of the measure within Duke Rheumatology. The central hypothesis is that Type 1 and 2 SLE are clinically distinct components of SLE that, once distinguished, will lead to improvements in the clinical management of SLE.

Methods:

Aim 1: Ensure the Type 1 and 2 SLE model matches the patient experience with lupus.

We will conduct a qualitative, descriptive study. For objective #1, we will conduct in-depth interviews. For objective #2, we will conduct cognitive interviews. In-depth interviews will be completed prior to cognitive interviews. Information learned in the in-depth interviews to develop patient-reported measures will be reviewed in the cognitive interviews.

In-depth interviews: During the in-depth interviews, participants will be asked to share their perspective on the experience with Type 1 and 2 SLE symptoms, treatments, and how their experience with lupus fits with the Type 1 and 2 SLE model. (See attachment for the question guide).

Cognitive interviews: Cognitive interviews determine how individuals process and respond to survey questions that were modified based on information learned during the in-depth interviews (Tourangeau 1984; Willis 2013). For our research, we seek to will learn how participants interpret each question and fit each symptom of the SLAQ and FSS into the Type 1 and 2 SLE model.

During the cognitive interviews, participants will be asked to describe how they responded to each survey question, how the question distinguishes between Type 1 and 2 SLE symptoms, and if there are any symptoms that are not currently included on the survey. The questions asked during cognitive interviews will be dependent upon the results of the in-depth interviews. Therefore, a question guide will be submitted as an amendment to the IRB prior to starting interviews.

In-depth interviews and cognitive interviews: The in-depth and cognitive interviews will be conducted by a trained interviewer on the telephone or in-person. They will each last about 1 to 1.5 hours and will be audio-recorded with an encrypted recorder. If an individual wishes to not be audio-recorded, detailed

notes will be taken instead. Demographic information will also be collected (see attachment for demographic questionnaire).

As a standard practice used in qualitative research, changes may be made to the question guide and demographic questionnaire during study preparation, training, pre-testing, and data collection to improve phrasing, probes, or the flow of questions or to add related questions. If the changes are within the overall topic domains or related topics currently described within this protocol, the revised questionnaire(s) will not be submitted to the IRB. If the changes fall outside of the current domains or related topics, we will submit the revised questionnaire to the IRB for review before implementation.

Inclusion: Individuals are eligible to participate if they have an established diagnosis of SLE and are followed in the Duke Lupus Clinic. Participants will be selected based on the extent of their Type 1 and Type 2 symptoms. These classifications will be based patient- and physician-reported measures from the prior visit to the Duke Lupus Clinic. We will exclude patients with significant cognitive impairment as determined by the treating rheumatologist.

Sample size:

In-depth interviews: We will conduct 12 to 15 interviews with individuals who experience higher Type 2 symptoms and 12-15 interviews with individuals who experience lower Type 2 symptoms. We chose these samples sizes because thematic saturation is typically reached around 12 interviews (Guest 2006). The interviewers will assess based on informational redundancy whether 3 additional interviews are needed.

Cognitive interviews: We will conduct at least two rounds of 10 cognitive interviews. Each round will include five participants who experience higher Type 2 symptoms and five participants who experience lower Type 2 symptoms. If further changes are necessary to the measures reviewed during the initial two rounds cognitive interviews, an additional six interviews will be conducted.

Participant selection and recruitment: We will purposefully select participants (Patton 2005) to identify the range of experiences. We will enroll a diverse study population with respect to 1) race (i.e., white and African American individuals) and 2) age (i.e., a range of ages, with an emphasis on recruiting young women). We will also stratified based on individuals' experience with higher versus lower Type 2 symptoms. These classifications will be based patient- and physician-reported measures from the prior visit to the Duke Lupus Clinic. High Type 1 symptoms will be defined as a SLEDAI score ≥ 6 (Gladman 2002). High Type 2 symptoms will be defined as a fibromyalgia severity score (widespread pain index + symptom severity index) ≥ 12 (Wolfe 2011).

Lupus Clinic is held each Wednesday in Duke South Clinic 1J. Prior to each weekly clinic, the patient list will be reviewed to identify potentially eligible patients. Eligibility will be determined based on information obtained from the medical record, as well as through a discussion with the individual's treating rheumatologist in the Duke Lupus Clinic. Prospective participants will be approached about the study during routine clinic visits at the Duke Lupus Clinic. The study will be introduced by the individual's Duke Rheumatologist.

Reimbursement: Participants will receive \$25 to reimburse them for their time participating in each interview.

Data Analysis: We will use descriptive statistics to summarize the demographic data and applied thematic analysis to analyze the qualitative data from the in-depth interviews and cognitive interviews.

In-depth interviews: Interviews will be audio-recorded and transcribed verbatim. Nvivo, a qualitative research software, will be used to facilitate analysis. First, we will each apply the same structural codes to group similar responses together. Thematic coding will follow, focusing on identifying the main themes and sub-themes for each conceptual group (Guest 2006). Intercoder reliability procedures will be conducted; discrepancies in coding will be discussed, resolved, and revised as necessary. Thematic code frequencies across transcripts will be examined to identify the most frequent and salient themes, and data

reduction techniques will be used to explore the nuances and to identify sub-themes. Descriptions of these themes and sub-themes, together with illustrative quotes, will be collected in data summary reports.

Cognitive interviews: After each interview, the interviewer will complete a debriefing form to identify 1) SLAQ modifications, and 2) Type 1 or 2 symptom assignment. The debriefing forms from each interview will be summarized after each set of 10 interviews to determine the main themes, problems with the patient-reported outcomes measures that arose during the interviews, and suggested modifications to the measures. Following the second round of interviews, it will be determined if an additional 6 interviews are needed to assess the revised measure.

Aim 2: Develop a preliminary parsimonious measure to rapidly assess Type 1 and 2 SLE activity.

We will analyze data collected through the Duke Lupus Registry (DLR) (IRB Pro00008875) and Sub-studies of the DLR (IRB Pro00094645). Working closely with the Duke Center for Health Measurement, [name] will use patient- and physician-reported data collected from 800 patient visits in DLR to develop an effective and efficient indicator of Type 1 and Type 2 SLE activity.

Data Collection: Age, gender, race/ethnicity, employment status, marital status, living arrangement, and medication adherence will be ascertained by self-report. In addition, the DLR collects information from medical records including: insurance, medication details, disease duration, and comorbidities. The DLR also collects the following information at each clinic visit:

- **Patient-Reported Measures:** Modified Systemic Lupus Activity Questionnaire (SLAQ), Fibromyalgia Severity Scale, Patient global assessment, current medications
- **Physician-reported measures:** Systemic Lupus Erythematosus Disease Activity Index (SLEDAI), Physician's Global Assessment, LFA-REAL
- **Routine Lupus Labs:** CBC with differential, creatinine, C3 and C4, anti-dsDNA antibody, C-reactive protein, sedimentation rate, complete urinalysis, and urine protein:creatinine

Data Analysis: Robust cluster analysis. [name] will expand on our preliminary cluster analysis using latent profile analysis to include detailed patient-, physician- and laboratory measures. **Power Calculation:** In order to identify 4 clusters using 8 predictive variables, a minimum sample size of 320 patients is needed. If the cluster analysis identifies 7 distinct clusters, there will be sufficient power to include 5 predictive variables in the model with 350 patients. Differences in phenotypes across clusters, including patients' demographic, SLE history, patient- and physician-reported measures, and laboratory tests will be estimated by ANOVA and Chi-squared test.

Using our new knowledge about the quantitative differences in SLAQ responses by cluster, the qualitative information about symptoms from patient interviews, and clinical expertise, we will revise the SLAQ and create a new scoring system with individual Type 1 and 2 SLE scores. This new scoring system will be tested using 800 patient visits to determine if the new Type 1 and 2 SLE scores correspond to cluster assignment. Using logistic regression models, [name] will compare three commonly used physician-reported SLE measures, the SELENA-SLEDAI, physician's global assessment, and LFA-REAL™ to determine if model fit improves with physician-reported measures. Goodness of fit will be assessed by the Hosmer-Lemeshow chi-square test, and model discrimination will be assessed using C statistics to estimate the area under the receiver operating characteristic curve. To account for patients potentially contributing more than one visit to this analysis, generalized estimating equations (GEE) will be used.

Inclusion: Patients who are enrolled in the Duke Lupus Registry and gave informed consent through the Duke Lupus Registry (DLR) (IRB Pro00008875) and Sub-studies of the DLR (IRB Pro00094645).

Compensation: Data collected from patients enrolled in the Duke Lupus Registry will be retrospectively analyzed. No compensation will be provided as part of this analysis.

Aim 3. Conduct a pilot implementation study of the Type 1 and 2 SLE model into clinical care.

To impact patients, the Type 1 and 2 SLE model needs to be translated into an actionable tool. The overall goal of Aim 3 is to develop and test a set of electronic medical record (EMR)-based tools that enable rheumatologists to assess, discuss, and treat Type 1 and 2 SLE.

Tool Development. Over the past year, the physicians in the Duke Lupus Clinic have organically developed approaches to assessing and discussing Type 1 and 2 SLE with their patients. [name] will work with the providers in the Lupus Clinic to iteratively create SLE@Duke, a set of EMR-based tools to implement the Type 1 and 2 SLE model into clinical practice. Components will include a templated lupus note, dotphrases to assess and explain Type 1 and 2 SLE, the PRO survey, patient handouts, and suggested treatment plans. [name] will assess provider satisfaction quarterly at the Lupus Clinic Meeting as SLE@Duke tools are tested in clinic, making iterative changes based on their feedback.

Pilot Testing. This aim will pilot the SLE@Duke program with the Duke Rheumatologists outside of the Duke Lupus Clinic, where an estimated one-third of Duke Rheumatology's SLE patients are seen by 11 rheumatologists and 4 nurse practitioners. Non-Lupus Clinic providers and patients will complete surveys to assess satisfaction with visits and the treatment of SLE.

Interventions. SLE@Duke. The components of SLE@Duke will be made available in Epic for providers to assess and discuss patients' Type 1 and 2 SLE activity at each clinic visit. Physician & Clinic Training will include Rheumatology Division Grand Rounds and in-person Academic Detailing sessions in each of the clinics. Accompanied by a Duke Lupus Clinic provider, [name] will make frequent visits to the rheumatology clinics at 1J, Brier Creek, and South Durham to introduce the surveys, educate the nursing staff and providers on Type 1 and 2 SLE, and troubleshoot any issues that arise. The goal of these visits will be to introduce SLE@Duke, as well as solicit feedback on how to improve the tool.

Outcomes & Evaluation. We will use the RE-AIM framework to guide our collection of comprehensive information about the reach, effectiveness, adoption, implementation, and maintenance of SLE@Duke (Table 1)²⁵.

Table 1: RE-AIM Framework for Implementation Assessment

Provider-Level Outcomes	Patient-Level Outcomes
REACH: participant characteristics; differences between participants & non-participants	

 - Frequency of rheumatologists using SLE@Duke¹ - Preference for paper vs EMR-based PRO² 	
 - Frequency of Paper vs EMR-based PRO completion¹ - Preference for paper vs EMR-based PRO³
EFFECTIVENESS: the impact of the intervention on outcomes of interest	

 - Appropriate Type 2 SLE Treatment¹ - Length of visits¹ - Physician satisfaction with visit² 	
 - Perceived quality of visit³ - Discussion of the Type 1 and 2 model³ - Understanding of lupus activity & treatment plan³
ADOPTION: proportion of the targeted population who initiate the intervention program	

 - % of lupus patients with assessment of Type 1 and 2 SLE in note¹ - % of lupus patients with treatment based on extent of Type 1 and 2 SLE¹ 	
 - % of patients who report discussion of the Type 1 and 2 model during visit³
IMPLEMENTATION: consistency of the delivery of the intervention	

 - Perceived benefits and barriers of SLE@Duke² - How SLE@Duke fit into or conflicted with work flow² - Impact of SLE@Duke on burden on CMAs² 	
MAINTENANCE: the long-term effects of the intervention program	

 - % of lupus patients with PRO in note at Month 1 vs. Month 6¹ 	

¹Collected from EMR; ²Collected from provider survey; ³Collected from patient survey

This assessment method measures the extent to which each of these components has been met and provides a framework for identifying facilitators and barriers. During a 6-month period, we expect to see approximately 260 SLE patients outside of the Lupus Clinic. Data will be collected from three sources: (1) Electronic Medical Record (EMR) will be utilized to determine if SLE@Duke is incorporated into visit documentation; (2) Provider surveys will assess whether and how the Type 1 and 2 SLE model is used,

satisfaction with visits, and perceived barriers and benefits of SLE@Duke; (3) *Patient surveys* will assess the quality of the visit, discussion of Type 1 and 2 SLE model, and understanding of lupus activity and treatment plan.

Inclusion: All clinic staff and providers in Duke Rheumatology are eligible. Patients are eligible to participate if they have an established diagnosis of SLE and are followed in Duke Rheumatology. We will exclude patients with significant cognitive impairment as determined by treating rheumatologist.

Consent Process

Aim 1 (qualitative): All participants will provide oral informed consent before participating in interviews. We are requesting a waiver of *written* informed consent (i.e., a signed consent form) under 45 CFR 46.117(c)(1), which states the following: *An IRB may waive the requirement for the investigator to obtain a signed consent form for some or all subjects if it finds...that the research presents no more than minimal risk of harm to subjects and involves no procedures for which written consent is normally required outside of the research context.*

Additionally, we anticipate that some of the interviews will be telephone interviews, making written informed consent logistically difficult. We will email the oral consent form prior to the interview, allowing potential participants to read and decline participation prior to their scheduled interview. We may also distribute the oral consent form to potential participants during recruitment. Before the interview is conducted, study staff will first obtain consent to participate in the interview. Each participant's ID number will be written on the oral consent form, and we will document in a study log that informed consent has been obtained from each participant.

Aim 2 (patient-reported outcomes measure): The consent will be obtained through the Duke Lupus Registry (DLR) (IRB Pro00008875) and Sub-studies of the DLR (IRB Pro00094645) and includes use of medical information.

Aim 3 (implementation): Details of the implementation will be dependent on our findings from Aims 1 & 2. An addendum to the IRB with details of the implementation will be submitted prior to start of this phase of the study. If consent is applicable, it will also be submitted through process of an amendment.

Subject's Capacity to Give Legally Effective Consent: Patients who are not competent to provide informed consent in English will not be included.

Study Interventions: To be determined based on findings from Aims 1 and 2.

Risk/Benefit Assessment: Being included in this study does not pose any increased risk to participants involved. There is minimal potential risk for loss of confidentiality. The data obtained, may improve the care for patients with SLE in the future. The risk to each participant in this study is no greater than minimal, making it reasonable given the potential benefit to future patients.

Costs to the Subject: None

Data & Safety Monitoring: A data monitoring committee will not be used.

Privacy, Data Storage & Confidentiality: All data including the audiotapes and transcriptions will be maintained on a secure server. Participants will be assigned a unique identification number that will not be related to their name, date of birth, social security number, or medical record number. For data analysis, the unique ID number will be the only patient identifier used.

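### Aim 2 is to deliver separate Type 1 and Type 2 scores, but its stated test, agreement with patient clusters, would also be passed by a single severity dimension

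*Combined protocol and SAP*

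**What the plan says.** Background & Significance states that "we have developed a new conceptual model that characterizes SLE activity into two dimensions". It faults the present SLAQ scoring for mixing the two types. The central hypothesis, in the same section, is worded differently: "The central hypothesis is that Type 1 and 2 SLE are clinically distinct components of SLE that, once distinguished, will lead to improvements" in clinical management.

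Under Aim 2, Data Analysis, the structural work is a latent profile analysis that "will expand on our preliminary cluster analysis using latent profile analysis to include detailed patient-, physician- and laboratory measures". Two sizes are given: "In order to identify 4 clusters using 8 predictive variables, a minimum sample size of 320 patients is needed", and "If the cluster analysis identifies 7 distinct clusters, there will be sufficient power to include 5 predictive variables in the model with 350 patients". Clusters are compared by ANOVA and chi-squared tests. The SLAQ is then revised into two scores using the cluster differences, the interviews and clinical expertise. The scores are tested on 800 visits "to determine if the new Type 1 and 2 SLE scores correspond to cluster assignment", using logistic models, the Hosmer-Lemeshow test, C statistics and GEE.

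The plan gives no factor or item-response model, no correlation between the two scores, no single-score comparator, no rule on profile shape and no level of C that counts as success. It does not say whether the logistic models are multinomial or one cluster against the rest.

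**The concern.** Latent profile analysis groups patients or visits. It does not ask how many dimensions the items have. If all symptoms rise and fall together, it returns ordered groups from mild to severe. Every item then differs between groups in the same direction, and any two sets of items, whatever their labels, give scores that follow the groups. The scores are also built partly from cluster differences and then checked against cluster assignment, so agreement is to be expected.

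The study could therefore report that the Type 1 and Type 2 scores correspond to clusters when both measure one thing. Cluster differences also could not show which score an item belongs to. Aim 3 builds the patient survey into record-based tools and counts patients whose treatment follows the extent of each type, so an untested split would carry into practice.

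**Working it through.** **The plan's own figures.** Both sizes equal 10 × clusters × variables: 10 × 4 × 8 = 320 and 10 × 7 × 5 = 350. The multiplier 10 is inferred. The sizes are not disputed; they are used below as the working scale.

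**Inputs.** From the plan: 8 variables, 350 patients, four or seven clusters, C statistic from logistic models. Assumed: 4 indicators labelled Type 1 and 4 labelled Type 2, normal, equal loadings, independent observations, and correlation r between the two factors. A single severity dimension is r = 1. There were 25 to 40 runs per setting.

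**Does finding several clusters point to two dimensions?** No. On one-dimensional data BIC chose on average 3.2, 4.3 and 5.4 profiles at loadings 0.6, 0.7 and 0.8. At loading 0.75 it chose 4, 5 or 6 profiles in 12, 16 and 2 of 30 runs.

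**Does the C statistic separate the cases?** Mean C for the two scores against cluster, loading 0.7, N = 350:

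| Setting | One dimension | Two dimensions (r = 0 to 0.5) |
|---|---|---|
| 4 clusters, multinomial | 0.999 | 0.999 |
| 4 clusters, one-versus-rest | 0.900 | 0.939–0.956 |
| 7 clusters, multinomial (r = 0 and 0.5) | 0.960 | 0.997–0.998 |
| 4 clusters, multinomial, scores share no items with clustering | 0.920 | 0.892–0.899 |
| 4 clusters, one-versus-rest, no shared items | 0.858 | 0.850–0.873 |

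At loading 0.6 the four-cluster multinomial C was 0.997 for one dimension and 0.996 for two. The lowest one-dimension value in any setting was 0.82 (seven clusters, one-versus-rest, no shared items). Nothing in the plan would treat these values as failure.

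**Would the ANOVA flag it?** No. The share of score variance explained by cluster (four clusters, loading 0.7) was 0.77–0.78 for one dimension and 0.64–0.68 for two.

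**Would the profiles show it?** Yes, if read for it. With four clusters, the largest Type 1 minus Type 2 gap within any cluster was about 0.07–0.16 SD for one dimension and 0.85–1.5 SD for two (r = 0 to 0.5).

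**Does a total-score comparator separate the cases?** With four clusters and a multinomial model, on one-dimensional data the two scores and the total both gave C = 0.999. On two-dimensional data at loading 0.75, r = 0.3 to 0.5, the two scores gave about 1.00 and the total 0.89–0.91. There are two limits, both seen at loading 0.7. With seven clusters, one-dimensional data gave 0.960 against 0.949, so a small gain is not evidence. With two clusters and r = 0.5, the total reached 0.996 against 0.999, so the comparator has little to detect.

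**Does a factor comparison separate them?** The two-factor model has one extra parameter, so BIC prefers it when the likelihood-ratio statistic exceeds ln(350) = 5.86. With N = 350, loading 0.7 and 60 runs each, the mean statistic was 0.4 at r = 1 (two factors chosen in 0% of runs). It was 33 at r = 0.85, 104 at 0.7, 218 at 0.5 and 300 at 0.3 (two factors chosen in 100% each time).

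**The case against.** The strongest reply is that Aim 2 sets out to develop a preliminary measure, not to count dimensions. Background & Significance also hypothesises activity states over time, including minimal and mixed periods, and profile analysis suits such states. The planned comparison of patient, physician and laboratory measures across clusters would show crossing rather than parallel profiles if two dimensions exist, and items are allocated with interviews and clinical expertise as well. All of this stands. It makes the gap one of a missing comparator and reading rule. It does not close it: interviews do not test dimensionality, and clusters that separate laboratory from self-reported findings may reflect who reported, not how SLAQ items divide.

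A reader might infer that a single dimension would pass at least as well, so that the result looks better when the model is wrong. The plan does not support that. It leaves the model form open and contemplates both four and seven clusters; with one-versus-rest models on shared items, or with seven clusters, one dimension generally scores lower. A reader might also infer that the central hypothesis itself asserts two dimensions. That wording belongs to the conceptual model; the hypothesis speaks of clinically distinct components and adds a claim about management.

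The simulation is idealised: normal indicators, equal loadings and, in the main case, scores built from the clustering variables. The rows without shared items show lower C values, but they still do not expose one dimension.

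**Conclusion.** The concern holds in limited form. Correspondence with cluster assignment cannot establish that two scores are warranted, because a single severity dimension also passes with high C statistics: about 0.996 to 0.999 under either truth with four clusters and a multinomial model, and 0.82 or more for one dimension in every setting tried. This rests on the assumed loadings, factor correlations, normality and independent visits, none of which the documents give. Repeat visits per patient were not simulated. The structural gap itself needs no simulation: the plan contains no item-level check, score correlation, comparator or profile rule. It should be fixed before the scores are built, but it does not invalidate a retrospective analysis for a preliminary measure.

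**What to change.** Add to Aim 2, Data Analysis, using the same registry visits:

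- A pre-specified comparison of one-factor and correlated two-factor models for the SLAQ and FSS items, treated as ordered, with patient-clustered standard errors.
- The Type 1/Type 2 factor correlation and score correlation, each with a 95% confidence interval.
- Use of the loadings, alongside interviews and clinical expertise, when assigning items to scores.
- A single total score as comparator in the correspondence models, with support for two scores claimed only if they predict cluster better than the total. State the model form and how the difference in C will be judged (for example, a confidence interval that respects repeat visits), since small gains can arise under one dimension.
- A sentence on how parallel and crossing profiles will be read.

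Keep the latent profile analysis as a description of patient groups. Read the factor result together with the physician and laboratory profiles: Type 1 is a set of signs in different organs that need not intercorrelate, and an analysis of self-report items alone can inflate the correlation. For that reason a fixed cut-off on the factor correlation, such as 0.85 to 0.90, should not be used as a gate.

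The cost is a wording change and a few days of analysis on data already held. The downside is that some items, or the split itself, may turn out not to be supported.
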